#### **4.3.1. Screening Visit, Observation Period (30 days ±2 days)**

The participant or his/her guardian must sign the informed consent form voluntarily in writing before participating in the screening. Approximately 330 participants will be screened for this study to allow approximately 240 participants to receive treatment of rimegepant.

The main procedures or tests to be completed by the participant at the Screening Visit include:

- Signing the informed consent form;
- Evaluation of inclusion/exclusion criteria;
- Collection of migraine history (signs/symptoms/frequency/intensity) and other medical history;
- Serum virological examination;
- Demographic information;
- Physical examination;
- Vital signs/physical measurements;
- Clinical safety laboratory tests;
- ECG;
- Urine routine;
- Urine drug screen;
- FSH (if applicable);
- Urine pregnancy;
- AE and SAE assessments;
- Dispense eDiary
- Install BYOD APP in the participant mobile phone.

The eDiary will be dispensed and BYOD APP will be installed after the participant has completed all screening procedures at the Screening Visit and the eDiary will be used to record migraine attacks and their severity on a daily basis during the Observation Period, as well as whether they received migraine treatment. BYOD will be used to record prophylactic or standard of care migraine medications/concomitant medications. Participants will be

trained in the use of eDiary and BYOD. Height in the physical measurements will only be measured at the Screening Visit. If a participant's WOCBP status has been confirmed in the BHV3000-310 trial, the participant is recognized to have the same status in this study and a repeat FSH test is not required.

During the Observation Period (30 days  $\pm 2$  days), the main procedures or examinations to be completed by the participant include:

- Recording prophylactic and standard of care migraine medications/concomitant medications via BYOD;
- AE and SAE assessments;
- Daily recording of migraine attacks and their severity by eDiary.

#### **4.3.2. Long-term Treatment Period (52 weeks)**

After completing the 30-day Observation Period, the participants will return to the clinical site for the Baseline Visit (Day 1). The main operations or examinations to be completed by the participants included:

- Evaluation of inclusion/exclusion criteria;
- Recording prophylactic and standard of care migraine medications/concomitant medications via BYOD;
- Physical examination;
- Vital signs/physical measurements;
- Clinical safety laboratory tests;
- Lipid panel
- ECG;
- Urine routine;
- Pregnancy test (urine and serum);
- AE and SAE assessments;
- Dispense study drug;
- Return eDiary and review eDiary and BYOD of completion for completeness;
- Daily recording of migraine attacks and their severity by eDiary;

- MSQoLQ version 2.1;
- MIDAS.

After the completion of the relevant items at the Baseline Visit (Day 1), before the participants take the study drug for the first time, the clinical site staff should confirm the eligibility of the participants for participating in the study based on the examination results at the Baseline Visit, and inform the participants by telephone of the eligibility results. The participants who meet all the inclusion criteria and do not meet the exclusion criteria can participate in the trial. Participants confirmed to be eligible by a telephone visit may start taking the study drug, rimegepant 75 mg (up to 1 tablet per day) at the time of a migraine attack (mild, moderate, or severe) and record the use of the study drug with BYOD.

Participants will make site visits at Weeks 4, 8, 12 ( $\pm 3$  days) and Weeks 16, 28, 40, 52 ( $\pm 3$  days) or Early Termination of the trial and telephone visits at Weeks 20, 24, 32, 36, 44, 48 for the Long-Term Treatment Period as follows:

- Recording prophylactic and standard of care migraine medications/concomitant medications via BYOD;
- Physical examination (Weeks 28 and 52 or early termination);
- Vital signs/physical measurements (at each site visit);
- Clinical safety laboratory tests (at each site visit);
- Lipid panel (at Weeks 28 and 52 or early termination);
- Electrocardiogram (at Weeks 28 and 52 or early termination);
- Urine routine (Week 52 or early termination);
- Urine pregnancy (at each site visit and at each telephone visit);
- AE and SAE assessments (at each site visit and at the telephone visit);
- Dispense study drug (at each site visit);
- Take the study drug;
- Record the use of study medication via BYOD;
- Return unused study drug for compliance check (at each site visit);
- Return eDiary and review eDiary and BYOD of completion for completeness (at each site visit);

- Daily recording of migraine attacks and their severity by eDiary;
- MSQoLQ Version 2.1 (at Weeks 12, 28, 40, 52, or early termination);
- Migraine PoM for migraine (Week 28 and Week 52 or at early termination);
- Satisfaction with Medication survey (Week 28 and Week 52 or Early Termination);
- CGI-c scale (at Weeks 28 and 52 or early termination);
- MIDAS (at Weeks 12, 28, 40, 52 or early termination).

Upon completion of the Baseline Visit, WOCBP will be provided with urinary pregnancy test kits so that participants can test at home if necessary. When WOCBP participants cannot confirm pregnancy status, a urine pregnancy test must be completed at home before taking study drugs.

During the treatment period, participants have to use the last bottle of study drug before opening a new bottle of study drug. Three wallets of study drug will be dispensed to the participants at each visit of Week 4, Week 8, and Week 12. Study drug will be dispensed at Week 16, Week 28, Week 40 visits as needed, the maximum dispensing limit for each visit is 7 bottles per participant. Study drug will be dispensed at site visits as needed. Dispensing of study drug may also occur at unscheduled visits as needed.

If a participant lacks 6 or more diary reports per month for 2 months (continuous or non-continuous), the participant's continued participation in the study should be terminated due to lack of compliance.

#### **4.3.3. End of Treatment (Week 52)**

Participants will have an End-of-Treatment Visit at Week 52 ( $\pm 7$  days) when they have completed the trial or at early termination. The site personnel will review the eDiary, assess concomitant medications, and complete participant safety tests (including physical examination, vital signs/physical measurements, clinical laboratory tests, lipid panel, pregnancy tests, and ECGs). Participants will return unused study drug and eDiray to the site.

#### **4.3.4. Safety Follow-up**

Participants will return to the clinical study site 14 days ( $\pm 2$  days) after the end of treatment. The main assessments or examinations to be completed for the participants include:

- Recording prophylactic and standard of care migraine medications/concomitant medications via BYOD;
- Vital signs/physical measurements;
- Clinical safety laboratory tests;

- ECG;
- Urine pregnancy;
- AE and SAE assessments;

Concomitant medications required for AEs and associated with AEs will be collected during the safety follow-up period.

#### **4.3.5. Unplanned Visit**

In consideration of the safety of the participants, the investigator may require the participants to conduct additional visits or examinations. Results of unscheduled visits or examinations will be recorded on the eCRF.

#### **4.3.6. End of Trial**

The end of the trial includes the completion of the trial and early termination of the trial. If either of these situation happens, the trial will be ended, and all participants will complete/discontinue from the trial with no further treatment.

Trial completion is defined as the time when the last participant completes the last visit and the sponsor has the right to terminate the trial at any timepoint throughout the trial for reasonable reasons.

Early termination of the trial implies that not all participants have completed all the scheduled procedures according to the protocol, and the entire trial or a part of the trial (such as a certain site) is terminated. The purpose of premature termination is to protect the rights and interests of participants, ensure the quality of the trial, and avoid unnecessary economic losses.

In general, the trial will not be terminated prematurely. However, the entire trial (or a certain site) can be terminated prematurely if any of the following situations occurs:

- 1 The total sample size is achieved as a result of competitive enrollment, while the site may have not completed the planned enrollment as per the contract or have completed the trial procedures for all of the participants;
- 2 The investigator in the site does not follow the protocol, Good Clinical Practice (GCP), etc.;
- 3 New information is received, which indicates unfavorable risk-benefit of the investigational drug, including sufficient evidence suggesting lack of efficacy or unacceptable safety;
- 4 The sponsor considers it to be inappropriate to continue the clinical trial for medical, ethical or business reasons;

- 5 Enrolling participants is slow, and it is impossible to complete the study within an acceptable time period;
- 6 The regulatory authority or ethics committee requests termination of the trial for certain reason.

#### **4.4. COVID-19 Emergencies**

If a participant is unable to come to the site for a visit due to the COVID-19 pandemic, it is acceptable to conduct remote visits on a case-by-case basis, but the investigator should first contact the sponsor medical monitor (or designee) to discuss the most appropriate of action. If a laboratory test is required for a remote visit, the local laboratory may be used in place of the central laboratory test results and the results are to be obtained and reviewed by the investigator. Direct shipment of study drug to participants via an overnight tracked and certified courier is also permitted with the approval of the sponsor in advance.

#### **4.5. Post-Study Treatment**

At the end of the study, the investigator should give the participant appropriate standard treatment recommendations for migraine.

### **5. PARTICIPANT POPULATION**

#### **5.1. Number of Participants**

Approximately 240 participants will be enrolled in this study. Participants who have participated in the BHV3000-310 study may be considered for this long-term safety study if they meet all of the criteria for this study, but this cannot be guaranteed.

#### **5.2. Inclusion Criteria**

##### **1) Signing Informed Consent**

- a) Written informed consent must be obtained from the participant in accordance with requirements of the study center's institutional review board (IRB) or ethics committee, prior to the initiation of any protocol-required procedures.

##### **2) Target Population**

Participant has at least 1 year history of migraine (with or without aura) consistent with a diagnosis according to the International Classification of Headache Disorders, 3rd Edition, beta version, including the following:

- a) Age of onset of migraines prior to 50 years of age
- b) Migraine attacks, on average, lasting 4-72 hours if untreated
- c) 6-18 migraine attacks of moderate or severe intensity per month within the last 3 months prior to the Screening Visit

- d) Six or more migraine days requiring treatment during Observation Phase
- e) Ability to distinguish migraine attacks from tension/cluster headaches
- f) Participants on prophylactic migraine medication are permitted to remain on therapy if the dose has been stable dose for at least 2 months prior to the Baseline Visit, and the dose is not expected to change during the course of the study. Participants who previously discontinued prophylactic migraine medication must have done so at least 5 half-lives of the prophylactic medication prior to the Screening Visit
- g) Participants with contraindications for use of triptans may be included provided they meet all other study entry criteria

### **3) Age and Reproductive Status**

- a) Male or female participants  $\geq 18$  years;
- b) Participant meets reproductive criteria. Refer to [Appendix 3](#) for reproductive criteria for male (Section [12.3.1](#)) and female (Section [12.3.2](#)) participants.;
- c) WOCBP must have a negative pregnancy test at the Baseline Visit prior to dispensing study drug;

### **4) Other Inclusion Criteria**

- a) No clinically significant abnormality identified on medical or clinical laboratory evalution. A participant with a clinical abnormality or laboratory parameters outside the reference range may be included only if the investigator considers the finding not clinically significant, that it will not introduce additional risk factors, nor interfere with the study procedures (not including the exclusion criteria listed in Section 5.3).

## **5.3. Exclusion Criteria**

### **1) Target Disease Exclusion**

- a) Participants has a history of basilar migraine with brain stem aura or hemiplegic migraine;

### **2) Medical History and Comorbidities**

- a) History of HIV disease
- b) Current evidence of poorly controlled, unstable, or recently diagnosed cardiovascular or cerebrovascular disease such as ischemic heart disease, coronary vasospasm, and cerebral ischemia. Myocardial infarction (MI),

acute coronary syndrome (ACS), percutaneous coronary intervention (PCI), cardiac surgery, stroke, or transient ischemic attack (TIA) during 6 months prior to screening;

- c) Poorly controlled hypertension (high blood pressure) or poorly controlled diabetes (but participants with stable hypertension and/or diabetes for at least 3 months prior to screening may be included in the study). Blood pressure greater than 150 mmHg systolic or 100 mmHg diastolic after 10 minutes of rest is exclusionary;
- d) Participants with a current diagnosis of major depression or a major depressive episode within the last 12 months, other pain syndromes, psychiatric disorders, dementia, or significant neurological disorders (other than migraine) that, in the opinion of the investigator, might interfere with study assessments;
- e) History of gastric or small intestinal surgery (including gastric bypass, gastric banding, gastric sleeve, gastric water ball, etc.) or diseases resulting in malabsorption;
- f) Participant has a history or diagnosis of Gilbert's Syndrome or any other active hepatic or biliary disorder;
- g) History or presence of significant and/or unstable medical conditions (e.g., history of congenital heart disease or cardiac arrhythmia, known suspected infection, hepatitis B or C or neoplasm) that, in the opinion of the investigator, would expose the participants to undue risk of a significant AE or interfere with the assessment of safety or effectiveness during the trial;
- h) History or evidence of alcohol or drug abuse within the past 12 months, or treatment for alcohol or drug abuse, or meeting Diagnostic and Statistical Manual of Mental Disorders, Fifth Edition (DSM-V) criteria for any significant substance abuse disorder within the past 12 months prior to the Screening Visit ;
- i) Participants should be excluded if they have a positive drug screen for drugs of abuse and are considered medically significant by the investigator, would compromise participant safety, or interfere with the interpretation of study results. In addition:
  - i. Participants with detectable levels of cocaine, amphetamines, and phenylcyclidine in drug abuse screening need to be excluded. Participants who are positive for amphetamines on the urine drug screen may have their urine samples evaluated for further analysis at the investigator's discretion to rule out a false positive result

- ii. Participants with detectable levels of marijuana during substance abuse screening may not be excluded if they do not meet DSM-V criteria for substance abuse or dependence in the participant's opinion as documented by the investigator, and a positive result does not signal a clinical condition that would impact the participant safety or interpretation of the study results.
- j) Diagnosis of hematologic or solid malignancy within 5 years prior to screening. Participants with a history of localized basal cell or squamous cell skin cancer may be included in the study if they are cancer-free prior to the Screening Visit for this study;
- k) Participants with a current diagnosis of schizophrenia, major depression requiring treatment with atypical antipsychotics, bipolar disorder or borderline personality disorder;
- l) Body mass index (BMI)  $\geq 35 \text{ kg/m}^2$ ;
- m) Participants with a history of gallstones or cholecystectomy;
- n) Use of St. John's Wort, products containing St. John's Wort, Coltsfoot root, or extracts within 14 days prior to the Baseline Visit;
- o) Use of narcotic drugs such as opioids (e.g., morphine, codeine, oxycodone, and hydrocodone) within 2 days prior to the Baseline Visit.

### **3) Allergy and Adverse Reactions**

- a) History of drug or other allergy that, in the opinion of the investigator, would make the participant unsuitable for participation in the study.

### **4) Sex and Reproductive Status**

- a) Women of childbearing potential who are unwilling or unable to use an acceptable method of contraception or avoid pregnancy by abstinence for the entire study period and for up to 28 days after last dose of study medication;
- b) Women who are pregnant or breastfeeding;
- c) Women who have a positive pregnancy test result at screening or prior to study drug administration;

### **5) ECG and Clinical Laboratory Test Findings**

- a) Estimated glomerular filtration rate (eGFR)  $\leq 40 \text{ mL/min/1.73 m}^2$  according to the re-expressed abbreviated (four-variable) Modification of Diet in Renal Disease (MDRD) study equation;

- b) Corrected QT interval  $> 470$  msec (QTc by method of Frederica) at Screening;
- c) Left Bundle Branch block;
- d) Right Bundle Branch Block with QRS duration  $\geq 150$  msec;
- e) Intraventricular Conduction Defects with QRS duration  $\geq 150$  msec;
- f) Serum bilirubin (Total, Direct or Indirect)  $> 1 \times$  ULN (Only abnormal values of between  $1-1.5 \times$  ULN may be repeated once for assessment of eligibility during the screening period);
- g) Neutrophil count  $\leq 1000/\mu\text{L}$  (or equivalent);
- h) AST or ALT  $> 1 \times$  ULN (Only abnormal values of between  $1-1.5 \times$  ULN may be repeated once for assessment of eligibility during the Screening Period.);
- i) Glycosylated hemoglobin (HbA1c)  $> 7\%$ .

## 6) Other Exclusion Criteria

- a) Prisoners or participants who are involuntarily incarcerated;
- b) Participants who are compulsorily detained for treatment of either a psychiatric or physical (e.g., infectious disease) illness;
- c) Lack of compliance and/or inability to complete the eDiary during the Observation Period. Lack of compliance was defined as more than 4 missed eDiary times during the Observation Period;
- d) Participation in a clinical trial with a non-biologic investigational drug (other than rimegepant) within 30 days prior to the Screening Visit;
- e) Participation in a clinical trial with a biological investigational drug within 90 days prior to the Screening Visit;
- f) Participation in any other investigational clinical investigators while participating in this clinical study.

### 5.4. Prohibited Concomitant Medications

The medications listed below are prohibited starting at the Baseline Visit and during the study or as specified:

- 1) St. John's Wort should not be taken 14 days prior to the Baseline visit and throughout the study;

- 2) Butterbur root or extracts should not be taken 14 days prior to the Baseline visit and throughout the study;
- 3) History of use of ergotamine medications on  $\geq 10$  days per month on a regular basis for  $\geq 3$  months;
- 4) Use of narcotic medication, such as opioids (e.g., morphine, codeine, oxycodone, and hydrocodone) was prohibited for at least 2 days prior to the Baseline Visit;
- 5) Use of acetaminophen or acetaminophen containing products for the treatment of non-headache symptoms is prohibited after the Baseline Visit. Any use of paracetamol or paracetamol-containing products for symptoms other than headache during the Observation Period must be discontinued at least 2 days before the Baseline Visit; paracetamol may be used during the Long-Term Treatment Period as a standard treatment for migraine, as described in Section 5.5.
- 6) Use of triptans is prohibited during the Long-Term Treatment Phase;
- 7) Use of marijuana is prohibited during the study;
- 8) Concomitant use of strong CYP3A4 inhibitors with rimegepant is prohibited during the study. If a strong CYP3A4 inhibitor is required (eg, with HIV protease inhibitors, hepatitis C protease inhibitors, certain azole antifungals, or clarithromycin), dosing with rimegepant should be stopped and should not start again until 14 days after the last dose of the strong CYP3A4 inhibitor. Please see [Appendix 1](#) Section 12.1.
- 9) Concomitant use of strong CYP3A4 inducers with rimegepant is prohibited during the study. If use of a strong CYP3A4 inducer is required (e.g., carbamazepine, phenytoin, or rifampin), rimegepant should be discontinued and not be resumed until 14 days after initiation of the strong CYP3A4 inhibitor. Please see [Appendix 1](#) Section 12.1.
- 10) Concomitant use of atypical antipsychotics such as Abilify® (aripiprazole), Zyprexa® (olanzapine), Seroquel® (quetiapine), Geodon® (ziprasidone) or Risperdal® (risperidone) or Depakote® /Depakene® (valproic acid/valproate) during the Long-Term Treatment Phase;
- 11) Concomitant use of LAMICTAL® (lamotrigine) is prohibited during the study.

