## **11. SUPPORTING DOCUMENTATION AND OPERATIONAL CONSIDERATIONS**

### **11.1. Ethical Conduct and Informed Consent**

#### **11.1.1. Review and Approval by Ethics Committee**

The Sponsor shall not carry out the clinical trial until obtaining the approval from the Ethics Committee. The sponsor/its authorized person should obtain the name and address of the Ethics Committee from the investigator and clinical trial institution, a list of Ethics Committee members participating in the project review, a review statement in compliance with GCP and relevant laws and regulations, as well as documents of approval from the Ethics Committee and other relevant materials.

After ethical review, if it is necessary to modify the protocol, informed consent form, and provide the participants and/or other relevant documents, the sponsor should first negotiate with the investigator and clinical trial institution, then modify the relevant documents and re-submit them to the Ethics Committee.

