- The investigator will be provided with investigational products that are easily identified, correctly coded, and specially labeled, and qualified. Investigational medicinal products should be appropriately packaged and stored as described in the trial protocol. The sponsor shall establish management system and record system for investigational drugs.
- The sponsor is responsible for assessing the safety of the investigational product during the drug trial. The sponsor shall timely notify the investigators, clinical trial institutions and drug regulatory authorities of the problems identified in the clinical trial that may affect the safety of participants, may affect the implementation of clinical trial and may change the approval comments of Ethics Committee.
- A qualified monitor will be appointed and accepted by the investigator.
- The sponsor and/or entrusted CRO shall establish quality control and quality assurance system for the clinical trial and may organize the audit on the clinical trial to ensure the quality.
- The sponsor shall specify the access to trial records. The sponsor should specify in the trial protocol or contract that the investigators and clinical trial institutions allow the monitors, auditors, reviewers of the ethics committee and inspectors from drug regulatory authorities to have direct access to source data and documents related to the clinical trial. The sponsor should confirm that each participant agrees in writing to the direct access of original medical records related to the clinical trial by the monitor, auditor, reviewers of the ethics committee and inspectors from drug regulatory authorities.
- The sponsor should designate a qualified medical expert to answer and consult the medical questions related to the clinical trial in a timely manner.
- The sponsor shall report adverse drug reactions as required and within the time limit.
- If the sponsor terminates or suspends the clinical trial in advance, the sponsor shall immediately inform the investigator, clinical trial institution and drug regulatory authority, and explain the reasons.
- The sponsor should take appropriate measures to ensure that compensation or indemnity can be provided to the participants and investigators. The sponsor shall provide legal and economic insurance or guarantee related to the clinical trial to the investigator and clinical trial institution, which shall be adapted to the nature and

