## 12. APPENDICES

## 12.1. Appendix 1 - Potent CYP3A4 Inhibitors and Inducers (Not All)

The following medications and concomitant medications are potent inhibitors of some CYP3A4. This list does not include all such drugs. Concomitant use of strong CYP3A4 inhibitors is prohibited as described in the study protocol.

Strong CYP3A Inhibitors
Boceprevir, cobicistat, konivaptan, danoprevir and ritonavir, etegavir and ritonavir, indinavir and ritonavir, itraconazole, ketoconazole, lopinavir and ritonavir, paraprevir and ritonavir (obitavir and/or dalatavir), posaconazole, ritonavir, saquinavir and ritonavir, telaprevir, teiranavir and ritonavir, troleandomycin, voriconazole, clarithromycin, nefazodone, neflifinavir

The following medications and supplements are strong inducers of some CYP3A4. This list does not include all such drugs. Concomitant use of strong CYP3A inducers is prohibited as described in the study protocol.

Strong CYP3A Inducers
Carbamazepine, phenytoin, rifampin, St. John's Wort

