at the first visit after EC approval (the PD will be regarded as Important if the updated ICF contains updated or important information on risk-related language”.

- The original B2 “Subject met exclusion criteria, but entered the study” corresponds to 1) -2 “Subject met exclusion criteria, but entered the study”.
- The original C2 “Study drug dose error (refer to protocol 7.2.2 and 7.2.3)” corresponds to 2) -2 “Error in study drug dose or method of administration, etc. (refer to protocol 7.2.2 and 7.2.3)”.
- The original C4 “Study drug was not stored or transported per protocol, and was administered to the subject before it was assessed as usable by the sponsor” corresponds to 2) -4 “Study drug storage issues (e.g., if subject was dispensed and used study drug with temperature excursions that has been deemed not usable or has not be confirmed as whether or not usable, it would be regarded as an Important PD. If subject was dispensed study drug with temperature excursions but did not use it, or used it after it was confirmed to be further usable, it would be regarded as a Non-important PD”.
- The original D1 “Subject used protocol-prohibited medications or therapies during the trial” corresponds to 3) -1 “Subject used protocol-prohibited medications or therapies”.
- The original E1 “Pregnancy test (if applicable) missing” corresponds to 4) -3 “Pregnancy test missing”.
- The original E2 “Subject entered study despite missing laboratory assessments or auxiliary examinations, etc., concerning the eligibility criteria” corresponds to 6) -3 “Study procedure or examination missing or incomplete (for indicators concerning the assessment of eligibility criteria or primary endpoint, if the procedure/examination has had an important impact on study results, e.g., where the procedure/examination was missing for more than 12 consecutive weeks, it would be regarded as Important)”.

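### Protocol 5.4 item 9 times the restart of rimegepant after a strong CYP3A4 inducer from the start of an inhibitor: the drug class is wrong, and the anchor probably is too

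*Protocol*

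**What the plan says.** Section 5.4 of the Protocol (Version 5.0) has two neighbouring rules on CYP3A4.

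- **Item 8, strong inhibitors.** If one is needed, "dosing with rimegepant should be stopped and should not start again until 14 days after the last dose of the strong CYP3A4 inhibitor".
- **Item 9, strong inducers.** It opens with a ban: "Concomitant use of strong CYP3A4 inducers with rimegepant is prohibited during the study". It then sets the trigger, "If use of a strong CYP3A4 inducer is required (e.g., carbamazepine, phenytoin, or rifampin", and ends with the restart rule: "rimegepant should be discontinued and not be resumed until 14 days after initiation of the strong CYP3A4 inhibitor".

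Both items send the reader to Appendix 1 (Section 12.1). The appendix lists carbamazepine, phenytoin, rifampin and St. John's Wort as strong inducers. On what to do about them it says only: "Concomitant use of strong CYP3A inducers is prohibited as described in the study protocol". It gives no restart interval, and neither does the SAP.

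**The concern.** The subject of item 9 is inducers from its first word to its examples, but the restart clock starts with an inhibitor. For a participant who has taken only an inducer, that event never happens and the 14 days cannot be counted. The literal result is that rimegepant is never resumed.

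The obvious repair is to swap the class word and leave the rest. That produces a clock running from the first inducer dose, which can expire while the inducer is still being taken and leaves little or no washout once it stops.

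This is operative dosing text. Rimegepant is taken as needed from supplies held at home, with up to 7 wallets dispensed at Weeks 16, 28 and 40 and only phone visits in between (Section 4.3, Table 1, and Section 4.3.2). The site therefore has to tell the participant when dosing may resume. Under item 9 it must guess or ask, and sites may repair the sentence differently.

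**Working it through.** There is no figure in the plan to reproduce. The check sets the texts side by side and then works out what each reading implies.

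**1. Drug class.** Item 9 names carbamazepine, phenytoin and rifampin, and Appendix 1 lists all three as inducers. No inhibitor enters item 9 until its last word. The class error is certain.

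**2. Anchor.** The documents do not state what was intended. Three places in the Protocol point to the last dose:

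- Item 8, the parallel rule, counts 14 days from the last dose.
- The first sentence of item 9 bans co-use. A clock started at initiation can run out during treatment with the inducer, so it does not work as a restart rule.
- St. John's Wort is on the inducer list in Appendix 1. Section 5.4 item 1 and exclusion criterion 2n in Section 5.3 bar it for 14 days before the Baseline Visit. For someone who stops it before baseline, this is a 14-day inducer-free interval before dosing. It is an entry rule, not a restart rule.

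**3. What each reading implies.** Let day 0 be the first inducer dose and D the number of days from first to last inducer dose. D is assumed.

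- Literal text: no restart date.
- Class corrected, initiation kept, co-use ban respected: earliest restart is about day max(14, D). Washout after the last inducer dose is max(14, D) − D = max(0, 14 − D).
- Last-dose anchor: restart on day D + 14, washout 14 days.
- Gap between the last two readings: (D + 14) − max(14, D) = min(D, 14), so at most 14 days.

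| D (assumed) | Restart, class-only correction | Restart, last-dose anchor | Gap (days) | Washout, class-only (days) | Washout, last-dose (days) |
|---|---|---|---|---|---|
| 7 | day 14 | day 21 | 7 | 7 | 14 |
| 14 | day 14 | day 28 | 14 | 0 | 14 |
| 28 | day 28 | day 42 | 14 | 0 | 14 |

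If the last inducer day itself is also excluded under the co-use ban, the class-only restart becomes max(14, D + 1). The D = 7 row does not change. For D of 14 or more, restart moves one day later, washout is 1 day and the gap is 13 days.

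**4. Reach into the analysis.** The deviation category in SAP Section 8.2, "Subject used protocol-prohibited medications or therapies", turns on whether a banned drug was used, not on the restart interval. The sample size and the planned summaries do not use the restart rule.

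**The case against.** The wording defect itself is hard to contest. The case on the other side is about weight.

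- **The two errors are not equally certain.** Nothing obliges item 9 to copy item 8, and no section states the intended anchor. This stands: the class error is certain, and the anchor error is an inference.
- **A careful site could find a cautious answer.** Item 8 sits directly above, and the St. John's Wort rule already gives a 14-day inducer-free interval. This stands in part. Both support the proposed repair, but neither is a restart rule for inducers, so the instruction still has to be corrected.
- **The arithmetic is hypothetical.** It rests on an assumed D and on a site that corrects the class but keeps initiation. That is true, and the table is an illustration only. The documents give no exposure, efficacy or safety effect of dosing soon after an inducer, so no harm can be quantified.
- **Safeguards exist.** The literal text leads to not dosing. Protocol Section 11.11 provides for medical queries: "The sponsor should designate a qualified medical expert to answer and consult the medical questions". Section 6.6 lets the investigator stop treatment. Entry exclusions 2d and 2g, on significant neurological disorders and unstable conditions, plausibly reduce the number who would need these inducers, although they depend on investigator opinion and apply only at entry. All of this stands and keeps the point minor.

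**Conclusion.** The point holds, as a minor one. As written, the restart clause of item 9 cannot be applied to the participants it is meant for, because it names the wrong drug class. Its anchor is probably wrong too, and the sponsor needs to confirm that.

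Those affected are participants who newly need a strong inducer, stop it, and wish to resume rimegepant within the 52 weeks. The documents give no count; it is probably small. Under a class-only correction the restart could come up to 14 days earlier than with a last-dose anchor, with 0 to 1 day of washout for courses of 14 days or more. These figures rest on the assumed D and on the co-use ban staying in force; with that ban, no reading permits overlapping use.

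**What to change.** Reword the restart clause of item 9 so that it names the right class and counts from the end of exposure, for example: *rimegepant must be stopped, and may restart only once 14 days have passed since the last dose of the strong CYP3A4 inducer*.

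Before issue, the sponsor's clinical pharmacology function should confirm both the last-dose anchor and that 14 days is the right interval for inducers. Item 8 and the St. John's Wort rule support both but do not settle them.

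The correction can go out as a protocol clarification or in the next amendment, with a notice to sites. Where the ethics committee must see it, Protocol Section 11.1.1 gives the route: agree the change with investigator and institution, "then modify the relevant documents and re-submit them to the Ethics Committee". The cost is one clause plus that administration. The SAP, the sample size and the deviation mapping need no change.
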